1.0 Objectives*

- 1.1 The purpose of this investigation is to determine the effect, if any, core activation and stabilization training may have on the gait and function of patients diagnosed with knee osteoarthritis (KOA).

The specific aims of this investigation include:

Specific Aim 1: Determine if kinetic (time to first peak ground reaction force [T_1] and second peak ground reaction force [F_2], both in the sagittal plane, and external knee adduction moment [KAM]) and kinematic (peak stance knee flexion angle [KFA]) gait variables, and speed, differ between patients with KOA and age and gender matched controls during self-selected paced ambulation, and determine which ones have predictive relationships with Knee Injury and Osteoarthritis Outcome Score (KOOS) scores in the patients with KOA.

Specific Aim 2: Determine if volitional core activation alters gait kinetics (T_1 , F_2 , and KAM), kinematics (KFA), and speed in patients with and without KOA during self-selected paced ambulation when compared to ambulating without volitional core activation, and whether the subjective pain complaints are significantly changed in the group with KOA. Determine whether there are baseline differences in core activation between those with and without KOA.

Specific Aim 3: Determine if a six-week core stabilization program alters KOOS score, and the kinetics (T_1 , F_2 , and KAM), kinematics (KFA), and speed of gait in patients with KOA during self-selected paced ambulation as compared to their pre-intervention baselines. Determine if there is a predictive relationship between the number of completed intervention sessions performed and these observed changes.

- 1.2 The alternate hypotheses for each specific aim include the following:

Specific Aim 1:

H_1 : Participants with KOA will have significant differences in lower extremity kinetics (T_1 , F_2 , and KAM) and kinematics (KFA), and gait speed, as compared to healthy controls during self-selected paced ambulation.

H_2 : The significant kinetic (T_1 , F_2 , and KAM), kinematic (KFA), and gait speed differences observed in participants with KOA will have a significant predictive relationship to their scores on the KOOS.

PROTOCOL TITLE: The Effects of Core Activation and Stabilization Training on Gait Kinetics, Kinematics, and Speed, and Self-Perceived Function in Patients with Knee Osteoarthritis

Specific Aim 2:

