2.0 Background*

- 2.1 This will be the second investigation by the PI and sub-investigator on this topic, following the promising results of a pilot study on a small sample size (N=5) completed last year. Whether or not core stabilization influences gait impairments in patients with KOA remains to be seen. Core stabilization has been shown to have positive effects, including increased stride velocity and scores on functional tests like the Functional Reach Test and Timed Up and Go, in older adults.¹ Older adults were also shown to have high compliance with a core stability training program.¹ A systematic

PROTOCOL TITLE: The Effects of Core Activation and Stabilization Training on Gait Kinetics, Kinematics, and Speed, and Self-Perceived Function in Patients with Knee Osteoarthritis

review indicated that core training is important to consider when treating older individuals to improve functional use of the extremities, improving participation in activities of daily living, and as part of a fall prevention program.² Additionally, it has been shown to benefit young, active individuals in preventing anterior cruciate ligament injury³ and greater duration of improved outcomes in patients with patellofemoral pain syndrome.⁴ Athletes with decreased core control have been shown to be at an increased risk of knee injury as well.⁵ One potential cause for this is the ability of the core to improve lower extremity kinematics when activated during challenging single leg weight bearing activity.⁶ A recent publication by Azuma, et al. did indicate that paraspinal and anterior abdominal thinning had a negative predictive relationship to the presence of KOA;⁷ however, no investigation has explored a cause and effect relationship between core stability/stabilization training and the presence or severity of KOA, nor the gait and functional ability of patients with KOA. This later concept is the focus of this investigation.

- 2.2 Unpublished pilot data (see 2.1) collected by the same PI and sub-investigator shows that volitional activation of the TA during self-selected paced ambulation significantly decreases the time to first peak ground reaction force (T_1) in the sagittal plane in participants with KOA ([name], [name], unpublished data, May 2018). This same kinetic gait variable is included in this investigation as one of the dependent variables in all three parts of the investigation.

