Once the set-up and calibration are completed, the data collection will begin. The participant will be allowed a brief warm-up of 1-2 minutes, walking in the Gait Lab prior to data collection commences. The participant will then be asked to walk at a self-selected pace across the capture area until three trials with good force plate contact are obtained. Good force plate contact is defined as initial contact at the heel and pre-swing/toe off occurring on the force plate, and the absence of any evidence of distraction via the video cameras, such as the participant talking or looking around the lab. These three trials will be used in the kinetic, kinematic, and gait speed data analysis.

See Part 2 for additional trials that will be performed concurrently for both groups. Participants in the experimental group will also be asked to complete a KOOS questionnaire at the same time.

Part 2: Participants will undergo the same procedures described in Part 1 above. While the three trials are obtained for Part 1, three additional walking trials will be concurrently collected for the both groups. These will include the participant volitionally activating their TA during the walking trials, performed and screened exactly the same as in Part 1. These trials will be performed with and without audible biofeedback (via an alarm or verbal cueing), indicating the TA meeting the threshold subsequently discussed below. Investigators will randomly determine whether the trials with or without volitional TA activation are performed first (i.e., Part 1 versus Part 2 trials). The randomization done for Part 2 to determine

PROTOCOL TITLE: The Effects of Core Activation and Stabilization Training on Gait Kinetics, Kinematics, and Speed, and Self-Perceived Function in Patients with Knee Osteoarthritis

whether or not the without (Part 1) or with (Part 2) volitional TA activation trials are performed first will be determined via random number generation between 0 and 1 in Excel. Those with 0 will perform the without volitional TA (Part 1) trials first, while those with 1 will perform the with volitional TA activation trials (Part 2) first.

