The patient will lie supine on the mat in the lab and will be taught how to perform a TA contraction. Please see the attached script with the instructions that will be used in this education. A baseline maximal contraction will be performed supine, and the amplitude of contraction will be considered maximal voluntary isometric contraction (MVIC). The device will be set to provide audible feedback, or the participant will receive a verbal cue from the investigator, at 30% MVIC. This feedback will be randomized throughout the trials with TA activation via random number generation in Excel, with 0 signifying no cue and 1 indicating a cue. The task will be repeated seated, then standing, prior to data collection.

The experimental group, during both sets of trials, will be asked to subjectively rate their perceived pain in the lower extremity being used in data collection via a 10-point scale, typically used on the NPRS, although no visual will be used. Please see the supplemental script document attached to this protocol for the instructions used.

Part 3: Participants in the experimental group will participate in a six-week core stabilization intervention program. Please see the attached intervention program. This program will commence as soon as possible after Parts 1 and 2 of the investigation are completed. Participants will participate in two scheduled intervention sessions each week. Additionally, there will be a home exercise program, consisting of exercises from each week to be performed at home independently. Participants will be provided education and a handout on these exercises by the PI, which will include directions, photographs of the exercises, and a completion check-off for each session. These will be performed three times per week, every other day. The PI will be coordinator of the scheduling and performance of these interventions. These intervention sessions will be performed in the RFP Clinic in the SAHP, either in the open gym or in a private treatment room. This decision will be left up to the participant. More than one participant may or may not undergo intervention with the PI simultaneously, but only with the participants' consent. No more

PROTOCOL TITLE: The Effects of Core Activation and Stabilization Training on Gait Kinetics, Kinematics, and Speed, and Self-Perceived Function in Patients with Knee Osteoarthritis

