than three participants will undergo the training simultaneously. Training sessions will not be performed on consecutive days in an effort to reduce the chances of delayed onset muscle soreness being present during treatment sessions. Additionally, the core training program includes predetermined guidelines on exercise progressions in order to ensure that the exercises are not progressed too rapidly. The PI will be present and will lead all sessions, ensuring that the exercises and their progressions are done correctly.

After the completion of the intervention program, each participant will undergo gait analysis in the same manner mentioned in Part 1, with the exception of no anthropometric data being collected.

Participants will then complete a second, post-intervention KOOS questionnaire, and turn in their home exercise program sheet with tallies from completed sessions. Please see Part 1 for completion of the pre-intervention KOOS questionnaire.

9.3 The table below details the procedures and occurrence of those procedures throughout a single participant's participation in the investigation:

Procedures	Occurrence
Education/Informed Consent	1 all participants
Anthropometric Data Collection	1 all participants
Baseline (Part 1) Without & With Core Activation (Part 2) Pre 6-Week Intervention Gait & EMG Assessment (Part 3)	1 all participants (except no part 3 for controls)
Pain NPRS Assessment	2 for KOA group
Core Stability Intervention Program	12 sessions, plus 18 home program sessions (KOA group only)
Post 6-Week Intervention Gait & EMG Assessment	1 (KOA group only)
Pre and Post 6-Week Intervention KOOS Assessment	2 (KOA group only)

9.4 The exclusion criteria serve to prevent participation of those who require assistance or assistive devices for ambulation, so safety during the ambulation activities is minimized. The adhesive tape used in reflective marker placement is intended for placement on the skin. Regarding PHI, the PI will be the only investigator involved in the recruitment and consent process and will be charged with

PROTOCOL TITLE: The Effects of Core Activation and Stabilization Training on Gait Kinetics, Kinematics, and Speed, and Self-Perceived Function in Patients with Knee Osteoarthritis

protecting the PHI in his office. The motion analysis data and PHI will be protected in the manner discussed in sections 11.3.

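### The Part 3 pre-test walks follow deliberate TA-activation walks for about half of the KOA group, while the post-test walks probably do not

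*Combined protocol and SAP*

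**What the plan says.** Section 9.2 (Part 2) collects three walks without and three walks with volitional TA activation in the same session, and no washout is stated. The order is drawn per participant: "Investigators will randomly determine whether the trials with or without volitional TA activation are performed first (i.e., Part 1 versus Part 2 trials". A draw of 0 puts the walks without activation first, and "those with 1 will perform the with volitional TA activation trials (Part 2) first".

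The section 9.3 table shows that this one visit serves all three parts: "Baseline (Part 1) Without & With Core Activation (Part 2) Pre 6-Week Intervention Gait & EMG Assessment (Part 3"), with one occurrence. The post-intervention row reads only "Post 6-Week Intervention Gait & EMG Assessment". For that visit section 9.2 (Part 3) says that "each participant will undergo gait analysis in the same manner mentioned in Part 1", without the anthropometric measurements.

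On teaching, section 9.2 has the TA contraction learned and rehearsed lying down, then adds: "The task will be repeated seated, then standing, prior to data collection". The Part 1 sequence in the same section (set-up, warm-up, three walks) contains no such step.

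The same walks also supply the baseline TA measure for Specific Aim 2: "Determine whether there are baseline differences in core activation between those with and without KOA". Section 11.1 names MANOVA, ANOVA or mean comparisons and mentions no order or period term.

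**The concern.** Randomising the order suits the Part 2 contrast, where both conditions are measured within one session. It suits a natural-gait pre-test less well. Aim 3 compares KOA participants with their own baseline and has no control arm, so a shift in the pre-test that is not matched at the post-test goes straight into the estimated training effect.

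There is a reason to take the possibility seriously for at least one outcome. Section 2.2 reports from the pilot that "volitional activation of the TA during self-selected paced ambulation significantly decreases the time to first peak ground reaction force", and T1 is an outcome in all three parts. If some of that effect persists when the participant is next asked to walk normally, pre-test T1 is lowered and a training-related decrease looks smaller than it is. If training does nothing, the same shift shows up as an apparent increase. For F2, KAM, KFA and speed the direction is unknown. Aim 3 H1 is non-directional, so errors both ways count.

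Part 1 is little exposed. Carry-over that is equal in the two groups cancels on average from the between-group difference, so bias there needs unequal carry-over or a chance imbalance in order.

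**Working it through.** **1. The plan's own figure.** 45 / (1 − 0.10) = 50, which matches the recruitment total in section 11.2. The 45 cannot be rebuilt, because alpha, power and effect sizes are not given. For the KOA group, 25 × 0.9 = 22.5, so 22 to 23 completers.

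**2. How many have the activation walks first.** Assume a fair 0/1 draw and block order as in section 9.2. Binomial(25, 0.5) has mean 12.5 and 95% range 8 to 17. Binomial(22, 0.5) has mean 11 and range 6 to 16.

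**3. Are there activation walks at the post-test?**
- Against: the baseline row of the table names walking without and with activation, and the post row does not. Pain is rated during both sets of walks, and the table lists two ratings in total for the KOA group, which the two baseline sets already use. No second order draw is described.
- For: the post-test follows the Part 1 manner, and the Part 1 text itself points to the additional Part 2 trials.
- Neutral: EMG in the post row proves nothing either way, because electrode placement is part of the Part 1 set-up.

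The balance favours no activation walks, but the text does not settle it.

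**4. Size of the shift.** Let A be the acute effect of activation and c the part of it that persists into later walks without activation. The documents give no value for c; 0%, 25% and 50% of A are assumptions.
- Mean pre-test shift = c × 0.5, which is 0%, 12.5% or 25% of A. With 8 to 17 of 25 activation-first it is 8–17% of A for c = 25% and 16–34% for c = 50%.
- Part 3, carry-over in the same direction as training: a true change equal to A is estimated at 100%, 87.5% or 75% of its size. A true change of A/2 is estimated at (0.5 − c/2)/0.5 = 100%, 75% or 50%. A true change of zero is estimated at 0%, 12.5% or 25% of A in the opposite direction.
- Part 2: activation-first participants show (1 − c)A and the others show A, so the average is (1 − c/2)A, or 100%, 87.5% or 75%. A period term does not alter this.

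**5. Consequence for the test** (two-sided 0.05, no Bonferroni correction, SD of change held constant).
- Masking: a paired test with 80% power (an assumption; section 11.2 states none) needs a standardised mean change dz of 0.626 with 22 completers or 0.611 with 23. Retaining 87.5%, 75% or 50% of the effect gives 69%, 56% or 29% power.
- Spurious change: with no training effect and 22 completers, carry-over of 0.2, 0.3 or 0.5 SD of the pre-post difference in activation-first participants gives rejection rates of 7.3%, 10.2% or 19.2%.

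**6. What analysis alone could recover.** Without-first participants have a pre-test free of activation-walk carry-over. About 11 completers at dz 0.62 give about 46% power.

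None of these figures covers TA teaching given to everyone before the baseline walks.

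**The case against.** The strongest reply is that nothing in the documents shows a deliberate contraction affecting gait once the instruction stops. The pilot statement concerns walking during activation, in five participants. This stands: the carry-over values are assumptions, and the 29% power figure needs both 50% carry-over and a training effect half the acute effect.

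Second, the cross-reference inside Part 1 can be read as bringing the activation walks and the order draw into the post-test. Carry-over would then cancel on average if equal at both visits. The table rows and the count of pain ratings make this the less likely reading, but it cannot be excluded. Even on it, the plan does not say whether the order is kept or redrawn, or whether TA teaching is repeated.

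Third, section 9.1 says that all condition trials are randomised, which could mean mixing walk by walk. Section 9.2 is more specific and sets block order; the figure of about half depends on that.

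Fourth, a reader might infer that a clean baseline is lost for good. The documents do not support that. Order is randomised, so without-first participants keep a pre-test unaffected by activation walks, at a price in precision. Only teaching placed before everyone's walks would remove that fallback, and section 9.2 is unclear on this.

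Finally, the instruction script and data-collection file are attachments not available here. They may specify rest periods or an instruction to walk normally between blocks.

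**Conclusion.** The point holds as a mismatch that the text makes likely, not as a demonstrated bias. One set of walks without activation serves as both the Part 2 comparator and the Part 3 pre-test; chance puts it after activation walks for about half of KOA participants; the post-test probably has none; and no order term is planned. The mean pre-test shift is about c/2, and zero if c is zero.

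Two stronger readings go too far. A reader might infer that the post-test certainly omits activation walks, but the Part 1 cross-reference leaves that open. A reader might also infer that the problem can only work against finding a benefit. That fits a T1 carry-over in the same direction as a training decrease, but not a non-directional hypothesis, nor the four outcomes whose direction is unknown.

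The conclusion rests on a fair draw, the block order of section 9.2 and the more probable reading of the post-test. A change is worth making because it is cheap and removes the dependence on an unknown quantity.

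**What to change.** 1. Record three acceptable natural-pace walks from every participant before any TA instruction. Use them for Part 1, the between-group baseline TA comparison and the Part 3 pre-test. Keep the randomised with/without blocks for Part 2. The maximal contraction can follow the new walks: section 9.2 limits the randomised cues to the activation trials, and earlier EMG can be normalised afterwards.
2. State that the post-test walks are taken before any TA instruction or activation walks at that visit. Align the Part 1, Part 2 and Part 3 text of section 9.2 and the section 9.3 table on when TA teaching occurs.
3. Include trial order in the Part 2 model, noting that it does not remove carry-over.
4. If the extra walks are not added, include order in the Part 3 change analysis and report the change for without-first participants, since averaging over both orders returns the shifted mean. Add a sensitivity analysis in without-first participants. This deals with activation-walk carry-over, not with teaching given to everyone, and has low power (about 46% with 11 completers at dz 0.62).

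**Cost.** At least three more acceptable walks per participant (six become nine), plus failed attempts; a slightly longer visit; possibly some added pain or fatigue in the KOA group before the pain ratings. No staff or equipment is added. If carry-over exists, the Part 2 contrast is still diluted.

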11.0 Data Management* and Confidentiality

- 11.1 Data analysis will be performed by the PI, with the assistance of the sub-investigator. The PI will use the latest version of SPSS available to the PI on his personal laptop computer (see 11.3 for security details). The kinetic, kinematic, and speed data will be analyzed together, either by a MANOVA (if assumptions are met) or separate ANOVA/mean comparison analyses with Bonferroni corrections, while the pain NPRS and KOOS scores will be analyzed each individually via means comparisons. The EMG data will be analyzed via a 2x2 ANOVA or separate means comparisons. If the groups have significantly different mean BMIs, then it will be included in the kinetic and kinematic analysis as a covariate. The predictive relationship between the number of exercise sessions and the change observed within the KOA group for each variable will be analyzed via regression analysis.
- 11.2 An *a priori* power analysis was performed to determine the number of participants required to achieve significance for the variables of highest interest in the investigation. Data from previous publications on these variables were used in the power analysis. These include the following: T₁ between¹⁶ and within ([name], [name], unpublished data, May 2018) groups, F₂ between and within groups,¹⁸ KAM between and within groups,¹⁷ KFA between¹⁴ and within²⁶ groups, and gait speed between¹⁶ and within²⁷ groups for the kinetic and kinematic analyses. Additionally, the KOOS²⁸ was examined for within-group means comparison. The PI used G*Power (Heinrich-Heine-University Düsseldorf, Düsseldorf, Germany) for the purposes of these analyses. It was determined that 45 participants would be required, except for the KFA which would require a larger sample size. Since this variable will be collected concurrently along with the other kinetic and kinematic data, and all the other variables of interest are appropriately powered at a much lower sample size, we felt confident proceeding regardless of being underpowered for one of these five dependent kinetic/kinematic variables of interest.

Since this study involves a six-week intervention, an attrition rate of 10% was assumed, so a total of 50 participants (25 healthy controls and 25 with KOA) will be recruited. Data analysis will be completed

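### The order of the with- and without-activation blocks is randomised by a simple 0/1 draw but used in no Aim 2 analysis; a stratified blocked list with a period adjustment is a low-cost gain in precision (minor)

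*Combined protocol and SAP*

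**What the plan says.** Section 9.2 Part 2 has every participant walk three accepted trials without volitional TA activation and three with it, in two blocks. Which block comes first "will be determined via random number generation between 0 and 1 in Excel". A draw of 0 puts the no-activation block first, "while those with 1 will perform the with volitional TA activation trials (Part 2) first". No blocked list is described, and no stratification by KOA or control.

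Section 11.1 gives the analyses:

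- Gait variables: a MANOVA, or separate ANOVAs or mean comparisons with Bonferroni correction.
- Pain: "while the pain NPRS and KOOS scores will be analyzed each individually via means comparisons".
- EMG: "The EMG data will be analyzed via a 2x2 ANOVA or separate means comparisons".
- Covariates: only one is named, and it is conditional. "If the groups have significantly different mean BMIs, then it will be included in the kinetic and kinematic analysis as a covariate".

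Order, sequence or period appears in none of these.

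Two other places bear on the same trials. Section 9.2 Part 2 describes TA teaching and the maximal contraction (MVIC), then says "The task will be repeated seated, then standing, prior to data collection". Section 9.2 Part 1 says "See Part 2 for additional trials that will be performed concurrently for both groups", and Part 3 refers back to Part 1 for the post-training gait session. In the section 9.3 table, the baseline row names both activation conditions and the post-training row does not.

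**The concern.** Randomising the order is sound and should stay. It implies that the second block may differ from the first for reasons unrelated to TA activation, such as warm-up or fatigue. If so, leaving order out of the analysis has two consequences. The block effect adds to the spread of the with-minus-without differences and so lowers power. And because the draw is unrestricted, one order may predominate by chance, which moves that trial's estimate by part of the block effect. With 25 per group, neither is automatically negligible, and both can be avoided at little cost.

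**Working it through.** **The plan's own figure.** Section 11.2 requires 45 participants and assumes 10% attrition: 45 / 0.9 = 50, or 25 per group, as stated. The 45 itself cannot be reproduced, because significance level, power and effect sizes are not given. Aim 2 is measured at the baseline session, so n = 25 per group is used.

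**Assumptions (not in the documents).** Each draw has probability 0.5. Effects are in SD of a person's with-minus-without difference. The true effect is 0.5 SD within a group and 0.8 SD for the KOA v control difference in change. Tests are two-sided at 0.05. The block effect b runs from 0 to 0.5 SD.

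**Model.** For person i, d_i = effect + b × s_i + e_i, with s_i = +1 if the no-activation block is first, −1 if the TA block is first, and e_i ~ N(0,1). At b = 0.5 the two orders therefore differ by 1.0 SD.

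**Chance imbalance.** For 25 people, P(16:9 or worse) = 2 × P(Binomial(25, 0.5) ≥ 16) = 0.2295, or 23%. For at least one of the two groups it is 1 − (1 − 0.2295)² = 0.406, or 41%. At 16:9 the unadjusted estimate shifts by b × (16 − 9)/25 = 0.28b, which is 0.14 SD at b = 0.5. False positives in that particular split are then 6.9%. Averaged over all splits they are 5.0%.

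**Loss of precision.** Under the unrestricted draw, order left out of the model gives Var(d) = 1 + b². At b = 0.3 the SD becomes √1.09 = 1.04, and at b = 0.5 it becomes √1.25 = 1.12. The standardised effect falls from 0.50 to 0.50/1.04 = 0.48 and 0.50/1.12 = 0.45.

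**Power by simulation (200,000 runs within group, 100,000 between groups).** The adjusted within-group test averages the two order-specific means with pooled variance on 23 df. The adjusted between-group test is an ANCOVA with order.

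| Block effect b | Within group: plan as written | Within group: blocked and adjusted | KOA v control: plan as written | KOA v control: blocked and adjusted |
|---|---|---|---|---|
| 0 | 67% | 67% | 79% | 79% |
| 0.1 | 67% | 67% | – | – |
| 0.2 | 65–66% | 67% | – | – |
| 0.3 | 63% | 67% | 76% | 79% |
| 0.5 | 57% | 67% | 70% | 79% |

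**Each half of the remedy alone.** Adjustment on an unblocked list gives about 65% within group and 78% between groups, whatever b is. Blocking without adjustment takes the block effect out of the estimate but leaves it in the residual SD, so the test is conservative: 3.0% false positives at b = 0.5 and 4.2% at 0.3. Its power at b = 0.5 is 54% or 61%, depending on which order receives the 13th person.

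**Form of the adjustment.** Let order add the same amount g to both of a person's values. The difference is (with + g) − (without + g) = with − without, so g cancels. An order main effect alone therefore leaves the within-person contrast unadjusted. The block effect enters the difference with opposite signs in the two orders, which is an order-by-condition term.

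**The case against.** **The plan is valid as it stands.** Random order keeps false positives at about 5.0% on average, and the 6.9% figure needs both an uneven split and a 0.5 SD block effect. This stands, and it is why the point is minor.

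**The larger gains need a large block effect.** At b = 0.5 SD the block trend is as big as the assumed treatment effect. Each block is three accepted walks after a warm-up, and nothing in the documents suggests a trend of that size. At 0.1–0.2 SD the gain is about 0–2 points. This stands too.

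**Section 11.1 does not name the factors of its MANOVA or 2x2 ANOVA, so silence on order may mean little.** This stands in part. The model is loosely specified throughout. But the EMG hypothesis in section 1.2 makes group and condition the natural two factors, a means comparison of pain scores has no place for order, and the only covariate named is BMI.

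**A stronger reading is tempting.** The no-activation trials also supply Aim 1 and, it appears, the Aim 3 baseline, and about half of participants would walk them after the activation block. A reader might infer that carryover contaminates all three aims. The documents do not support that: they give neither evidence of carryover nor its size. Nor would the adjustment proposed here remove it. Splitting Aims 1 and 3 by order would leave about 12–13 per group at baseline, too few to inform.

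**Conclusion.** The point holds as a minor one. Order is randomised without balance within group and is then unused in the Aim 2 analyses. The consequence is lost precision and exposure to an uneven split. A reader might take it to mean that the Aim 2 results are biased or their error rate inflated; averaged over the randomisation, they are not.

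Under the stated assumptions, the remedy gains nothing measurable at block effects of 0–0.1 SD, about 4 points within group at 0.3 SD and about 10 at 0.5 SD. For KOA v control change the gains are about 3 and 9 points at 0.3 and 0.5 SD. All of this depends on a block effect that the documents do not quantify.

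Two matters need clarification only. It is not settled whether participants who start with the no-activation block are taught the TA contraction before those trials, since the teaching text sits under Part 2; the attached scripts, not available here, may answer this. And the text and table differ on whether the post-training session includes activation trials.

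**What to change.** 1. **List.** Draw order from a blocked 1:1 list stratified by KOA and control, giving 13:12 in a group of 25.
2. **Analysis.** State in section 11.1 that the Aim 2 gait, pain and EMG analyses adjust for order as a period effect: either order as a factor on each person's with-minus-without difference, or order together with its order-by-condition term in the repeated-measures model. Adopt this together with the blocked list.
3. **Limit.** Say that this removes a block effect and not carryover.
4. **Clarify.** State whether TA teaching and MVIC come before the no-activation trials of those who start with that block. Reconcile Part 3's reference back to Part 1 with the post-training row of the section 9.3 table, so that the baseline and post-training sequences are the same for Aim 3.

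**Cost.** A different Excel list, a short addition to section 11.1, one degree of freedom, and a simple model in place of the pain means comparison. If there is no block effect, the power loss is under 0.5 points with the blocked list, and about 2 points within group (67% to 65%) if the list stays unblocked. Blocking makes some orders predictable, which matters little because everyone performs both conditions; mixed block sizes limit it. No extra visits, trials or participants are needed.
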